- 9. Tumor assessments: Appropriate spiral CT with contrast (preferred method) or MRI scans will be conducted at screening and Day 22 ± 5 days of every even cycle for the first 6 months (Cycles 2, 4, 6) and then every 12 weeks (Cycles 9, 12, 15, etc.) until disease progression or subject's End of Treatment visit. Scans at the End of Treatment visit will be performed if not done within the prior 8 weeks unless additional anticancer therapy has been initiated or if a tumor assessment is required for the confirmation of response. Subjects who discontinue treatment for reasons other than disease progression should continue tumor assessments until disease progression, withdrawal of subject's consent or initiation of another anticancer therapy. If subject is allergic to IV contrast, MRI scans or non-contrast CT may be used. The imaging schedule (every 8-12 weeks) should be maintained regardless of dosing delays or additional imaging assessments performed. Tumor scans will be reviewed by the clinical sites. Tumor assessments may be conducted locally for convenience; however, efforts should be made to decrease the variability of the assessments. An independent review of tumor scans may be conducted if deemed necessary by the Sponsor for the assessment of the efficacy of tipifarnib. Copies of tumor images must be de-identified of subject's personal information at the clinical sites and provided to the Sponsor or its designee if an independent review is requested by the Sponsor.
- 10. Subjects will receive tipifarnib starting at 600 mg orally bid with food on days 1-7 and 15-21 of 28 day treatment cycles.
- 11. Buccal swabs will be collected at screening for CXCL12 SNP testing and as a control sample for the analysis of tumor mutations using kits provided by the Sponsor. If swabs are not collected during screening for any reason, collection can be conducted at any time during the study. Detailed buccal swab collection, storage and shipping procedures will be provided in a separate lab manual.
- 12. An End of Treatment visit will be conducted within 30 days (+/- 7 days) from the last dose of tipifarnib or immediately before the initiation of any other anticancer therapy.
- 13. Complete physical exam will be performed at screening within 14 days of first administration of study drug and at the End of Treatment visit. A symptom-based physical exam will be conducted on Day 1 of every treatment cycle.

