Cohort 3 is added as part of Amendment 4 to the protocol to include subjects who have SCC with HRAS mutations. The purpose of this cohort is to explore tipifarinib's anti-tumor activity in HRAS mutation positive SCCs independent of tissue origin.

Only consented subjects who meet all the eligibility criteria will be enrolled in the study. All screening evaluations will be completed within 4 weeks (28 days) of Cycle 1 Day 1. Any screening evaluation, including disease status, will need to be repeated if performed more than 4 weeks from Cycle 1 Day 1. Efforts will be made to collect information on the response and duration of response of the subject's last prior therapy.

Up to 75 evaluable subjects may be enrolled in the study. A two-stage study design will be used separately in Cohort 1 and in Cohort 2 in order to minimize the number of study subjects treated if tipifarnib were considered not sufficiently efficacious to grant further development in this subject population. This design is intended to allow the termination of accrual in a particular study cohort in case of unacceptably low efficacy after objective responses in the first 11 evaluable subjects (Stage 1) in the cohort are assessed in a Full Analysis Set (FAS) basis. If no objective responses are observed in a cohort after the first 11 evaluable subjects, the cohort will be closed to further enrollment. If two or more responses are observed in the cohort, 7 additional subjects will be enrolled (Stage 2). Treatment will be considered of further interest if at least 4 responses are observed in a cohort (out of 18 subjects). Tumor response assessments will be conducted according to RECIST v1.1 criteria (confirmation of response is required), but in order to expedite the response assessment of the initial 11 evaluable subjects, tipifarnib will be considered not sufficiently efficacious if no confirmed objective tumor responses are observed in the study cohort prior to 6 months from the time of enrollment of the last of the 11 evaluable subjects.

In Cohort 2, upon observation of 4 confirmed responses, enrollment of HRAS mutant HNSCC subjects will continue up to 30 subjects with HRAS mutant HNSCC (10 enrolled in Stage 1 and 2 combined, plus 20 additional subjects) to further explore the antitumor activity of tipifarnib in this tumor type.

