Tumor assessments will be performed at screening and approximately every 8 weeks starting at the end of cycle 2 for the first 6 months (Cycles 2, 4, 6) and then every 12 weeks (Cycles 9, 12, 15, etc.), or sooner if deemed necessary by the Investigator, and will continue until disease progression. A tumor assessment will be performed upon treatment discontinuation (End of Treatment visit) if the reason for discontinuation is other than disease progression and no tumor assessment was performed in the prior 8 weeks, or a tumor assessment is required for the confirmation of response to treatment. Subjects who discontinue treatment for reasons other than disease progression must continue tumor assessments until disease progression, withdrawal of subject's consent or initiation of another anticancer therapy. Determination of objective tumor response will be performed by the Investigator. However, tumor images may be de-identified of subject's personal information at the clinical sites and collected by the Sponsor or designee to undergo an external independent radiological review if the sponsor deems it necessary for the final assessment of the efficacy of the treatment. If an independent radiological review were to be conducted, reviewers would be blinded to Investigator's tumor response assessments. An independent review committee charter would be generated to provide the specific procedures that would be filed with Institutional Review Board (IRB) and regulatory authorities.

Subjects with a solitary site of disease who have experienced a response may be considered for surgical resection. Subjects with a Partial Response (PR) and residual disease after salvage surgery are eligible to continue on study therapy.

Upon disease progression, all subjects in the study cohort will be followed approximately every 12 weeks for survival and the use of subsequent therapy until either death or 12 months after accrual in the subject's study cohort has been completed, whichever occurs first. Information on survival and subsequent anticancer therapy may be collected by phone.

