9.2. Exploratory Efficacy Analyses

The duration of objective response (DOR) will be calculated for subjects who achieve CR or PR. For such subjects, the DOR is defined as the number of days from the start date of PR or CR (whichever response is achieved first) to the first date that progressive disease is objectively documented. Disease progression will be determined by the Investigator using RECIST (version 1.1). The DOR will be right-censored at the date for subjects who achieve CR or PR and meet 1 of the following conditions: 1) when non-protocol anticancer treatment started before documentation of disease progression, 2) when death prior to documented disease progression or documented disease progression after more than 1 missed disease assessment visit, or 3) when alive and does not have documentation of disease progression before a data analysis cutoff date. (Therefore, analysis cutoff date will be used as the censoring date).

Progression free survival (PFS) will be defined as the time (in months) from first dose (Cycle 1 Day 1) to either first observation of progressive disease or occurrence of death due to any cause within 126 days (approximately 2 time intervals for tumor assessments) of either first administration of tipifarnib or the last tumor assessment. Observation of progressive disease can be by either documented radiographic progression (i.e., scan results) or documentation of symptomatic or clinical progression agreed upon and documented by investigators. In subjects without a progression date or with a death date more than 126 days after the first administration of study drugs or the last tumor assessment, the PFS time should be censored on the date of last tumor assessment or date of first administration of study tipifarnib. PFS analyses should consider tumor assessments after treatment discontinuation or metastatic surgery.

The DOR and PFS, will be summarized descriptively using the Kaplan-Meier (KM) method. The 25th, 50th, and 75th percentiles of the Kaplan-Meier distribution will be used to describe the median response duration and median PFS.

The median DOR and PFS and corresponding pointwise 95% confidence interval will be displayed by cohort for the FAS population and for the PP population, and for the subgroups.

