The KM curves of DOR and PFS by each cohort will be displayed for the FAS population, the PP Population, and for the subgroups in figures. A per subject summary of DOR, such as treatment initiation date, progression date, first response date, durations, censoring status, best overall response, and analysis population inclusion, will be provided. Similarly, a per subject summary of PFS, including enrollment date, treatment initiation date, progression date, duration, censoring status, best overall response, and analysis population inclusion, will also be provided.

Subgroup analysis may be conducted to estimate PFS and DOR in the subset of subjects with partial response. Sensitivity analysis may be conducted to assess the impact of the median survival estimation method. Interpolation based estimates can be used to estimate the median

Protocol KO-TIP-001

survival whenever the sample size is small or there is not sufficient information (events) to robustly estimate the median survival based on KM function.

Further analysis may include the comparison of the PFS between tipifarnib and prior therapies. A *P* value comparing the two PFS profiles (prior therapy and the current using tipifarnib) will be obtained using Wei-Lin (Cox regression based) robust estimator.

If biomarkers including somatic mutations in archival tumor tissue have been successfully obtained for enough subjects, the relationship of the detection of tissue biomarkers potentially related to tipifarnib activity will be investigated as described in the protocol.

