14. CHANGES IN THE STATISTICAL METHODS FROM THOSE STATED IN THE PROTOCOL

Overall survival was added as an additional analysis.

Included sensitivity analysis for PFS and DOR on a subset of subjects.

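### PFS from first dose among partial responders (optional in SAP 9.2) includes the event-free wait needed to join the subset, so its median exceeds the cohort median by construction

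*SAP*

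**What the plan says.** SAP 9.2 allows, without requiring, an extra look at responders: "Subgroup analysis may be conducted to estimate PFS and DOR in the subset of subjects with partial response". It names no landmark, no time-dependent handling of response and no caveat on interpretation.

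The same section sets the two clocks differently. For PFS: "Progression free survival (PFS) will be defined as the time (in months) from first dose (Cycle 1 Day 1". For response duration: "the DOR is defined as the number of days from the start date of PR or CR (whichever response is achieved first". It displays median PFS by cohort for the FAS and PP populations and for the subgroups, all summarised descriptively by Kaplan-Meier.

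On response, SAP 4.1 states: "Tumor response assessments will be conducted according to RECIST v1.1 criteria (confirmation of response is required". Protocol 8.1 and 10.1 also require confirmation. SAP 9.1, which defines best overall response for the ORR, does not repeat the word confirmed, and neither does the sentence on the partial-response subset.

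On timing, SAP 4.1 schedules scans "approximately every 8 weeks starting at the end of cycle 2 for the first 6 months (Cycles 2, 4, 6", and note 9 to Table 1 of the protocol synopsis fixes the day as "Day 22 ± 5 days of every even cycle for the first 6 months (Cycles 2, 4, 6". The synopsis also lets the investigator add scans when needed or to confirm a response.

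SAP Section 14 lists, as a change from the protocol: "Included sensitivity analysis for PFS and DOR on a subset of subjects". It does not say which subset.

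**The concern.** Being a partial responder is not a baseline characteristic. It is acquired weeks after the PFS clock starts, and only by subjects who have not yet progressed or died. Anyone with an early event is excluded from the subset by that event, while everyone in it is credited with the wait. This is guaranteed-time (immortal-time) bias.

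The subset median could sit in the report next to the cohort median. A reader who compares the two would see a longer PFS in responders and could credit it to response or to tipifarnib, although a gap of this kind appears even when response has nothing to do with progression.

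**Working it through.** **Plan's own figures.** The documents state no PFS figure, so there is none to reproduce on this point. The trial's only calculated design is the two-stage ORR rule (stop at 1 or fewer of 11, fail at 3 or fewer of 18). It reproduces by exact binomial enumeration: 0.0875, 0.8001, 0.6974 and 0.1130, against the stated 0.087, 80%, 0.697 and 0.113. It is not an input here.

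**Inputs from the documents.** 28-day cycles; scans on Day 22 (±5) of Cycles 2, 4 and 6; PFS from Cycle 1 Day 1; 30.4375 days per month (SAP 7.1).

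**Assumptions.** Exponential PFS; cohort median m of 3 to 12 months; response unrelated to progression; a 28-day gap where an extra confirmation scan is used (the documents give no minimum gap).

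**Step 1: event-free time L built into membership, for a response first seen at the first scheduled scan.**
- Unconfirmed PR at Cycle 2 Day 22: 28 + 22 = Day 50; 50/30.4375 = 1.64 months.
- Confirmed by an extra scan 28 days later: Day 78; 78/30.4375 = 2.56 months.
- Confirmed at Cycle 4 Day 22: 3 × 28 + 22 = Day 106; 106/30.4375 = 3.48 months.

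These are nominal. At the early edge of the window, Days 45 and 101 give 1.48 and 3.32 months, and unscheduled scans could shorten the wait further.

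**Step 2: effect on the median.** With S(t) = 2^(−t/m), the median among subjects still event-free at L solves 2^(−(t−L)/m) = 1/2, so t = m + L. The relative excess over the cohort median is L/m.

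| Assumed cohort median (months) | L = 1.64 | L = 2.56 | L = 3.48 |
|---|---|---|---|
| 3 | 4.64 (+55%) | 5.56 (+85%) | 6.48 (+116%) |
| 4 | 5.64 (+41%) | 6.56 (+64%) | 7.48 (+87%) |
| 6 | 7.64 (+27%) | 8.56 (+43%) | 9.48 (+58%) |
| 12 | 13.64 (+14%) | 14.56 (+21%) | 15.48 (+29%) |

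**Step 3: simulation on the scan grid.** Two million subjects were simulated with response independent of progression. Responses were first seen at scans 1, 2 and 3 in an assumed 70/20/10 split and confirmed at the next scheduled scan. Subset medians were 7.01, 10.20 and 16.22 months for cohort medians of 3, 6 and 12. These exceed the Day 106 column because later first responses require a longer wait. Dating progression at the next scheduled scan moves both medians to scan days but keeps the gap: for a true median of 6 months, 8.08 in everyone against 10.84 in the confirmed subset.

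**Step 4: does the membership rule cause the gap?** Re-analysing the same subjects from Day 106, the residual median in those confirmed by then against non-responders still at risk was 3.00 vs 3.00, 5.99 vs 6.00 and 11.98 vs 12.00 months. The excess disappears once the clock starts after membership is fixed.

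**The case against.** The analysis is optional, exploratory and descriptive. As a plain description of how long partial responders remained progression-free, the number is computable and not wrong. It is too long only relative to the cohort median or under a causal reading, and the per-subject DOR summary in SAP 9.2 gives first response dates, so an alert reader can see the wait. All of that stands, and it keeps the point minor. It does not remove the problem, because FAS median PFS is displayed too and nothing warns against setting the two side by side.

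Four stronger readings are tempting, and the documents do not support them:

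- **That a comparison of responders with non-responders is planned.** SAP 9.2 specifies no such test or contrast.
- **That 3.5 months is guaranteed.** It assumes confirmation at the Day 106 scan. Extra scans, the ±5-day window, or counting unconfirmed PRs shorten the wait. If unconfirmed PRs count, about 1.6 months remains with scheduled scans.
- **That Section 14 labels this analysis a sensitivity analysis.** It mentions only an unnamed subset. SAP 9.2 calls the partial-response analysis a subgroup analysis and uses the sensitivity label for the method of estimating the median. The link is likely but not stated.
- **That DOR shares the fault, or that complete responders are lost.** DOR starts at response, so it leaves out the wait from first dose; only the interval from response to confirmation stays built in. The main DOR analysis already covers CR and PR.

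**Conclusion.** The point holds at low severity. PFS from first dose in partial responders includes event-free time that the subset's entry rule demands, so its median exceeds the FAS median by construction and cannot be read as a drug effect or as the benefit of responding. The direction follows from the documents. The size does not: the range of about +14% (1.6 months, median 12) to +116% (3.5 months, median 3) rests on exponential PFS, response unrelated to progression, a first response at the first scheduled scan, and assumed cohort medians. Later first responses raise it; early or extra scans lower it. The ORR decision and the two-stage rule are unaffected.

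**What to change.** In SAP 9.2, delete PFS from the sentence on the partial-response subset. Describe responders by DOR for all CR plus PR, as already defined there, and add time to response if wanted. The cost is SAP wording only. Protocol 12.2.1 contains no PFS analysis in responders, so nothing it promises is lost.

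In SAP Section 14, state which subset is meant. If it is this one, do not call it a sensitivity analysis: selecting subjects on outcome tests no assumption of the FAS PFS analysis.

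Only if PFS by response is wanted, pre-specify a landmark at a fixed study day after the Cycle 4 Day 22 window closes (106 + 5 = Day 111), for example Day 112. Include subjects event-free on that day, group them by confirmed CR or PR by then, and count time from the landmark. State the price:

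- Subjects with earlier events are dropped. With an assumed exponential median of 4 months, 2^(−3.48/4) = 55% remain at Day 106, so about 45% are lost. At Day 112 (3.68 months), 53% remain. At Day 106 the loss is about 55% if the median is 3 months and 18% if it is 12.
- With a 4-month median, about 10 of 18, 11 of 20 or 16 of 30 subjects would remain at Day 106, before splitting by response.
- Subjects who respond after the landmark count as non-responders.

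In cohorts this small, deletion is the better choice.

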9.3. Other Efficacy Analyses

Per subject data on detail of tumor burden marker, and on subsequent therapy and survival status will be displayed in listings.

Waterfall figures and spider plots will illustrate best overall percent change in tumor burden (defined as sum of diameters) for the FAS population, the PP population and by subgroup.

An analysis of overall survival to estimate median overall survival time and corresponding 95% confidence interval and provide per subject summary of overall survival will be conducted. Overall survival will be defined as the time (in months) from first dose (Cycle 1 Day 1) to the occurrence of death due to any cause. In subjects without a death date, the OS will be censored on 1) the last date of survival status if alive, 2) a data analysis cutoff date for subjects with no survival status documentation, or 3) the date a subject withdraws consent or is lost to follow-up, if there is no additional information.

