The evaluations to be performed during the study are summarized in Table 1.

Table 1: Schedule of Activities

Activity	Screening	Day 1 ¹⁶	Day 7 ¹⁷ (± 2 days)	Day 22 (± 5 days)	End of Treatment Visit ¹²	Follow Up Visit ¹⁴	Follow Up Contact ¹⁵
ICF, Inclusion/exclusion criteria evaluation, Collection of HRAS mutation information	X						
Demographics and medical history, including HPV status and information on prior anti-cancer therapy(ies)	X						
Concomitant meds and AE assessment ¹	X	X	X	X	X	X^{18}	
12-Lead ECG ²	X						
ECOG performance status	X^4	X			X		
Physical Exam ¹³	X^4	X			X		
Weight	X^4	X			X		
Height	X						
Vital Signs (temperature, blood pressure heart rate)	X^4	X	X		X		
Hematology ³	X^4	X^5	X ⁵		X		
Blood chemistry ³	X^4	X ⁵	X ⁵		X		
Coagulation ³	X ⁴						
Urinalysis ^{3, 6}	X ⁴						
Tumor blocks or slides for HRAS ⁷	X						
Pregnancy test ⁸	X ¹⁹	X ²⁰			X		
Tumor assessment (CT scan or MRI) ⁹	X			X	X	X	
Tipifarnib administration ¹⁰		X					
Buccal swab ¹¹	X						
Collection of survival and anticancer treatment information						X	X

^{1.} Assessed throughout the course of the treatment and approximately 30 days after treatment discontinuation. Additional assessments may be performed until AE resolution or the adverse event is deemed irreversible by the Investigator. Collect AE (only) on Day 7.

^{2. 12-} Lead ECG is performed during screening within 14 days of first administration of study drug. Additional ECGs may be performed if deemed necessary by the Investigator.

^{3.} Fasting for chemistry testing is not required. Laboratory tests may need to be conducted on additional time points if deemed necessary by the Investigator. Samples will be analyzed locally at the clinical site or its reference laboratory. Laboratory assessments may be repeated if values are borderline to inclusion level or may change due to best supportive care measures.

^{4.} Assessment must be done within 14 days prior to first administration of study drug on Day 1 of Cycle 1.

^{5.} Laboratory tests do not need to be repeated on Cycle 1 Day 1 if they were conducted within 72 hours prior to the first dose of tipifarnib. Dehydration, creatinine elevations and hypokalemia have been described with tipifarnib treatment. A serum

- chemistry test will be conducted at Day 7 ± 2 days and hydration and electrolyte imbalances, if observed, corrected according to institutional guidelines. Additional follow up tests may be conducted at the discretion of the investigator.

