Tumor assessments will be performed at screening and approximately every 8 weeks starting at the end of cycle 2 for the first 6 months (cycles 2, 4, 6) and then every 12 weeks (cycles 9, 12, 15, etc.), or sooner if deemed necessary by the Investigator, and will continue until disease progression. A tumor assessment will be performed upon treatment discontinuation (End of Treatment visit) if the reason for discontinuation is other than disease progression and no tumor assessment was performed in the prior 8 weeks, or a tumor assessment is required for the confirmation of response to treatment. Subjects who discontinue treatment for reasons other than disease progression must continue tumor assessments until disease progression, withdrawal of subject's consent or initiation of another anticancer therapy. Determination of objective tumor response will be performed by the Investigator. However, tumor images may be de-identified of subject's personal information at the clinical sites and collected by the Sponsor or designee to undergo an external independent radiological review if the sponsor deems it necessary for the final assessment of the efficacy of the treatment. If an independent radiological review were to be conducted, reviewers would be blinded to Investigator's tumor response assessments. An independent review committee charter would be generated to provide the specific procedures that would be filed with IRB/ECs and regulatory authorities.

Subjects with a solitary site of disease who have experienced a response may be considered for surgical resection. Subjects with a Partial Response (PR) and residual disease after salvage surgery are eligible to continue on study therapy.

Upon disease progression, all subjects in the study cohort will be followed approximately every 12 weeks for survival and the use of subsequent therapy until either death or 12 months after accrual in the subject's study cohort has been completed, whichever occurs first. Information on survival and subsequent anticancer therapy may be collected by phone.

All subjects will be followed-up for safety during treatment and up to approximately 30 days (30 +/- 7 days) after treatment discontinuation or until immediately before the initiation of another anti-cancer therapy, whichever occurs first. Additional follow up may be implemented until the

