11.7.1 Follow Up after Disease Progression

Upon disease progression, all subjects will be followed approximately every 12 weeks for survival and the use of subsequent therapy until either death or 12 months after accrual in the subject's study cohort has been completed, whichever occurs first. Information on survival and subsequent anticancer therapy may be collected by phone.

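### SAP 9.3 censors overall survival at the data cutoff when survival status is undocumented; this credits unobserved time, can bias OS only upward, and has no stated precedence over the rule for lost or withdrawn subjects

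*SAP*

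**What the plan says.** SAP 9.3 defines the endpoint: "Overall survival will be defined as the time (in months) from first dose (Cycle 1 Day 1) to the occurrence of death". A subject without a death date is censored at one of three dates:

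- rule 1: "1) the last date of survival status if alive"
- rule 2: "2) a data analysis cutoff date for subjects with no survival status documentation"
- rule 3: "3) the date a subject withdraws consent or is lost to follow-up, if there is no additional information"

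No order of precedence is given.

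Survival status comes mainly from follow-up contacts. Protocol 8.1 states: "Upon disease progression, all subjects in the study cohort will be followed approximately every 12 weeks for survival". SAP 4.1 repeats this. Protocol 11.7.1 runs the contacts "until either death or 12 months after accrual in the" subject's cohort is complete. The Table 1 row "Collection of survival and anticancer treatment information" is marked for the Follow Up Visit as well as the Follow Up Contact.

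For a subject who stops treatment without progression and starts another anticancer therapy, the documents say two things. Protocol 8.1 and 10.1, Table 1 note 9 and SAP 4.1 let tumor assessments end at the new therapy. Protocol 11.7 has them continue until progression.

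OS is not a protocol objective. SAP section 14 lists it as an added analysis.

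**The concern.** Rules 1 and 3 stop the clock at a date tied to something recorded about the subject. Rule 2 stops it at a date on which, by its own condition, nothing is known. A subject censored this way stays in every risk set up to the cutoff but cannot contribute a death.

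Elsewhere the SAP uses observed dates for comparable purposes. PFS is censored at the last tumor assessment or first dose (SAP 9.2), and ongoing adverse events are closed at death or last contact (SAP 10.1).

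The trial is single-arm with small cohorts. A median OS will be read at face value, with no control arm in which the same artefact would show.

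**Working it through.** **1. Figures to reproduce.** The documents give no expected median OS, event count or loss share, so there is no OS figure to check. The design figures concern response rate only. They reproduce by exact binomial calculation (stage 1: 11 subjects, stop at 1 or fewer responses; final: 18 subjects, failure at 3 or fewer). The stopping probability is 0.697 at 10% and 0.113 at 30%; power is 0.800; alpha is 0.0875 against the stated 0.087. The OS rule does not enter any of these.

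**2. Which subjects reach rule 2.**

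| Subject without a death date | Source of status | Rule |
|---|---|---|
| Progressed, in 12-weekly contact | Survival contacts | 1 |
| Recorded as lost or withdrawn, with a survival record | Record plus exit date | 1 or 3 |
| Recorded as lost or withdrawn, no survival record | Exit date only | 2 and 3 both fit |
| Off treatment, no progression, no new therapy | Follow-up visits every 8 to 12 weeks (Protocol 11.7) | 1 if status is recorded there |
| Off treatment, new therapy, no progression | Documents conflict; contacts are tied to progression | 2 possible |
| On treatment at the cutoff | Cycle visits | 2 possible, adding only the time since the last visit |

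Rows three and five matter. In row three the programmer can choose between two dates. In row five, adverse-event reporting also ends at the new therapy (Protocol 10.9), and nothing requires the subject to be recorded as lost.

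**3. Direction.** The Kaplan-Meier estimate is S(t) = Π(1 − d_j / n_j) over death times up to t. Moving a censoring date later leaves every d_j unchanged and can only keep or raise n_j. Each factor therefore stays the same or rises, and S(t) and the median cannot fall. In the simulations below the median was lower in no trial.

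**4. Size, by assumption.** None of these inputs is in the documents except the cohort sizes of 20 (Cohort 3) and 30 (HNSCC).

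*Model A, early loss:* N = 30, exponential survival, cutoff uniform at 12 to 48 months after entry, lost subjects last seen uniformly at 2 to 6 months, 4,000 trials per setting. *Model B, loss throughout:* large sample, exponential survival and loss, 36 months of uniform accrual, cutoff 12 months after the last entry. The true median is 12 months in both. Entries are Kaplan-Meier medians in months; for Model A, the median across trials.

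| Share lost | A: all under rule 2 | A: half under rule 3 | B: all under rule 2 | B: half under rule 3 |
|---|---|---|---|---|
| 5% | about 12.0 | about 11.9 | 12.3 | 12.2 |
| 10% | 12.5 | about 12.3 to 12.4 | 12.5 | 12.5 |
| 20% | 14.0 | about 13.3 | 13.4 | 13.0 |
| 30% | 16.1 | about 14.3 | 15.2 | 13.3 |

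Censoring the same subjects at last contact gives medians between 11.8 and 12.1 throughout. Repeat runs of Model A differ by 0.1 to 0.2 months. As a proportion, Model A with all under rule 2 gives 12.5/12 − 1 = 4% at 10% lost and 16.1/12 − 1 = 34% at 30%.

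In a single small cohort the median often does not move. Under Model B with a true median of 9 months and all lost subjects under rule 2, it rose in 1%, 6%, 30% and 62% of trials at 5%, 10%, 20% and 30% lost with N = 20. With N = 30 it rose in 2%, 16%, 55% and 83%.

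**The case against.** A reader might infer that survival follow-up starts only at progression, that everyone lost from view is counted as alive to the cutoff, and that the median OS is therefore inflated. The documents do not support that.

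- Rule 3 names loss to follow-up as well as withdrawal and censors at that date. Protocol 8.4 lists loss to follow-up as a reason for withdrawal and requires contact attempts to be documented. **This stands**; it limits rule 2 to subjects with no survival record and, depending on precedence, no recorded loss.
- Only the 12-weekly contacts start at progression. Before that, subjects are seen each cycle or at follow-up visits, and Table 1 marks survival collection there. **This stands in part.** The assessment list in Protocol 11.7 omits survival, and Table 1 note 14 requires those visits only when tumor assessments are done. The mark does not help a subject whose assessments ended at a new therapy.
- Protocol 11.7 keeps assessments going after a new therapy, so progression may still be found and the contacts triggered. **This stands** against any claim that they are never triggered. What remains is an unreconciled conflict with Protocol 8.1 and SAP 4.1.
- The end of contacts 12 months after cohort accrual creates no rule 2 subjects: those followed until then have a status, and rule 1 applies. **This stands.**
- OS carries no hypothesis, and SAP 9.3 promises per-subject OS summaries. **This stands** on consequence: a careful reader could see the censoring, but the reported median would still rest on it.

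**Conclusion.** Rule 2 is wrong as written: it credits survival time that nobody observed, and its boundary with rule 3 is undefined. The direction of any bias is certain, because the OS curve and median can only be unchanged or raised.

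The size is not known, because the documents do not give the share of subjects under rule 2. On the stated assumptions it runs from near nil at 5% to about 4 months on a true median of 12 at 30%. That upper figure needs every lost subject to be under rule 2 and last seen by month 6. It is a conditional risk; inflation has not been shown. The response-rate analysis and the two-stage decision are untouched. The point is worth correcting because the repair is small and a single-arm median OS invites direct reading.

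**What to change.** In SAP 9.3, replace the three rules with one: censor every subject without a death date at the last date known alive from any source (visit, dose, scan, laboratory sample, adverse event, survival contact), no later than the cutoff. Report the number censored by reason. A single rule also removes the precedence question.

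Reconcile Protocol 8.1 and SAP 4.1 with Protocol 11.7 on follow-up after a new therapy without progression, and state how survival status is obtained for that group.

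*Cost.* The SAP change is one sentence and a derived date from data already collected. The reported median OS may be shorter. A change to protocol follow-up is a formal amendment needing ethics approval (Protocol 12.5). It cannot repair data already cut: SAP 7.2 names cuts of April and September 2020, and the SAP is dated January 2021. The SAP change does not depend on it and can be made alone.
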